10.1.2 Methods and Timing for Capturing and Assessing Safety Parameters

The physician is responsible for ensuring that all AEs collected as per protocol (see Section 10.1.1.1 for definition) are recorded in the AE section of the CRF and reported to the marketing authorization holder in accordance with instructions provided in this section and in Section 10.1.3.

For each AE recorded in the AE section of the CRF, the physician will make an assessment of seriousness (see Section 10.1.1.2), severity (see Appendix 3), and causality (see Appendix 3).

10.1.2.1 Adverse Event Reporting Period

Physicians will seek information on AEs at each patient contact. All AEs subject to the collecting and reporting requirements outlined in this protocol, whether reported by the

patient or noted by study personnel, will be recorded in the patient's medical record and in the AE section of the CRF.

Once the patient is enrolled in the study, AEs will be collected until the end of his or her observation period. After this period, the physician is not required to actively monitor patients for AEs but if the treating physician becomes aware of any related AEs to any medicinal product they should be notified to the competent authority in the Member State where the reactions occurred or to the marketing authorization holder of the suspected medicinal product, but not to both (to avoid duplicate reporting).

10.1.2.2 Procedures for Recording Adverse Events

Physicians should use correct medical terminology/concepts when recording AEs in the AE section of the CRF. Colloquialisms and abbreviations should be avoided.

Only one AE term should be recorded in the event field of the CRF.

See Appendix 3 for further specific instruction regarding:

- Diagnosis versus signs and symptoms
- Adverse Events occurring secondary to other Adverse Events
- Persistent or recurrent Adverse Events
- Abnormal Laboratory Values
- Abnormal Vital Sign Values
- Abnormal Liver Function Tests
- Deaths
 - All events with an outcome or consequence of death should be classified as serious adverse events (SAEs) and reported to the marketing authorization holder immediately. All deaths that occur during the protocol-specified AE reporting period, regardless of relationship to study medicine, must be recorded in the AE section of the CRF and immediately reported to the marketing authorization holder
- Pre-existing Medical Conditions
- Lack of Therapeutic Efficacy or worsening of Malignant Melanoma
- Hospitalization or Prolonged Hospitalization
- Overdoses, Misuses, Abuses, Off-Label Use, Occupational Exposure, or Medication Error
- Drug Interactions
- Quality Defects and Falsified Medicinal Products

10.1.3 Reporting Requirements from Physician to Marketing Authorisation Holder

10.1.3.1 Immediate Reporting Requirements from Physician to Marketing Authorization Holder

Certain events require immediate reporting to allow the Marketing Authorization Holder and the regulatory authorities to take appropriate measures to address potential new risks associated with the use of the medicine. The physician must report such events to the marketing authorization holder immediately; under no circumstances should reporting take place more than 24 hours after the physician learns of the event. The following is a list of events that the physician must report to the marketing authorization holder within 24 hours after learning of the event, regardless of relationship to study medicine:

- SAEs
- Non-serious AEs of special interest
- Pregnancies

The physician must report new significant follow-up information for these events to the marketing authorization holder immediately (i.e., no more than 24 hours after becoming aware of the information). New significant information includes the following:

- New signs or symptoms or a change in the diagnosis
- Significant new diagnostic test results
- Change in causality based on new information
- Change in the event's outcome, including recovery
- Additional narrative information on the clinical course of the event

For reports of SAEs and non-serious AEs of special interest, including follow-up, physicians should record all case details that can be gathered immediately (i.e., within 24 hours) in the AE page of the CRF and submit the report via the EDC system. A report will be generated and sent to Roche Drug Safety by the EDC system.

In the event that the EDC system is temporarily unavailable, please refer to Section 10.1.3.3.

Physicians must also comply with local requirements for reporting SAEs to the local health authority and IRB/EC.

10.1.3.2 Reporting Requirements for Non-Serious Adverse Events

For all non-serious AEs, including follow-up reports, physicians must record all case details that can be gathered within 30 calendar days of learning of the event on the AE section of the CRF and submit the report via the EDC system. A report will be generated and sent to Roche Drug Safety or the relevant marketing authorization holder (for non-Roche studied products) to allow appropriate reporting to relevant competent authorities.

In the event that the EDC system is temporarily unavailable please refer to Section 10.1.3.3.

10.1.3.3 If EDC System is Temporarily Unavailable or not Used

In the event that the EDC system is {temporarily unavailable} a completed paper reporting form and fax coversheet should be faxed/scanned to Roche Drug Safety or its designee immediately (i.e., no more than 24 hours after learning of the event) or within 30 days for non-serious AEs if not AEs of special interest, using the fax number or email address provided to physicians.

Once the system is available again, all information should additionally be entered and submitted via the EDC system.

10.1.3.4 Reporting Requirements for Pregnancies/Breastfeeding Pregnancies/Breastfeeding in Female Patients

Female patients of childbearing potential will be instructed to immediately inform the physician if they become pregnant during the study or within 30 days after the last dose of medicine. A Pregnancy Report should be completed by the physician immediately (i.e., no more than 24 hours after learning of the pregnancy and sent to Roche Drug Safety. Pregnancy should not be recorded on the AE CRF. The physician should discontinue Cobimetinib and Vemurafenib and counsel the patient, discussing the risks of the pregnancy and the possible effects on the fetus. Monitoring of the patient should continue until conclusion of the pregnancy. Any SAEs associated with the pregnancy (e.g., an event in the fetus, an event in the mother during or after the pregnancy, or a congenital anomaly/birth defect in the child) should be reported on the AE section of the CRF.

Suspected adverse reactions that occur in infants following exposure to a medicinal product from breast milk should be reported to Roche Drug Safety.

Pregnancies in Female Partners of Male Patients

Male patients will be instructed through the Informed Consent Form to immediately inform the physician if their partner becomes pregnant during the study or within 30 days after the last dose of study medicinal product. A Pregnancy Report should be completed by the physician immediately (i.e., no more than 24 hours after learning of the pregnancy) and sent to Roche Drug Safety. Attempts should be made to collect and report details of the course and outcome of any pregnancy in the partner of a male patient exposed to study medicine. The pregnant partner will need to sign an Authorization for Use and Disclosure of Pregnancy Health Information to allow for follow-up on her pregnancy. Once the authorization has been signed, the investigator will update the Pregnancy Report with additional information on the course and outcome of the pregnancy. A physician who is contacted by the male patient or his pregnant partner may provide information on the risks of the pregnancy and the possible effects on the fetus, to support an informed decision in cooperation with the treating physician and/or obstetrician.

Abortions

Any abortion should be classified as an SAE (as the marketing authorization holder considers abortions to be medically significant), recorded in the AE section of the CRF, and reported to the marketing authorization holder immediately (i.e., no more than 24 hours after learning of the event; see Section 10.1.3.1).

Congenital Anomalies/Birth Defects

Any congenital anomaly/birth defect in a child born to a female patient exposed to the medicine {or the female partner of a male patient exposed to the medicine} should be classified as an SAE, recorded in the AE section of the CRF, and reported to the marketing authorization holder immediately (i.e., no more than 24 hours after learning of the event; see Section 10.1.3.1).

10.1.3.5 Reporting Requirements for Adverse Events originating from Patient Reported Outcomes

Although sites are not expected to review the PRO data, if physician/study personnel become aware of a potential adverse event during site review of the PRO questionnaire data, he/she will determine whether the criteria for an adverse event have been met and, if so, these must be reported using the Adverse Event (e)CRF.

10.1.4 Follow-Up of Patients after Adverse Events

10.1.4.1 Physician Follow-Up

The physician should follow each AE until the event has resolved to baseline grade or better, the event is assessed as stable by the physician, the patient is lost to follow-up, or the patient withdraws consent. Every effort should be made to follow all SAEs considered to be related to studied medicinal product until a final outcome can be reported.

During the study period, resolution of AEs (with dates) should be documented in the AE section of the CRF and in the patient's medical record to facilitate SDV.

All pregnancies reported during the study should be followed until pregnancy outcome.

10.1.4.2 Marketing Authorization Holder Follow-Up

For all AEs, the Marketing authorization holder or a designee may follow up by telephone, fax, electronic mail, and/or a monitoring visit to obtain additional case details and outcome information (e.g., from hospital discharge summaries, consultant reports, autopsy reports) in order to perform an independent medical assessment of the reported case.

10.2 SAFETY REPORTING REQUIREMENTS FOR NON-STUDIED MEDICINAL PRODUCTS

Although adverse event information is not being actively solicited for non-studied medicinal products, the physician/consumers are reminded to report any adverse reactions (for which they suspect a causal role of a medicinal product) that come to their attention to the marketing authorization holder of the suspected medicinal product, or to the concerned competent authorities via the national spontaneous reporting system.

In addition, the following should also be reported if occurring during exposure to a marketed medicinal product, even in the absence of adverse events:

- Pregnancy
- Breastfeeding
- Abnormal laboratory findings
- Overdose, abuse, misuse, off-label use, medication error or occupational exposure
- Reports of lack of efficacy
- Product quality defects and falsified medicinal products
- Data related to a suspected transmission of an infectious agent via a medicinal product

- Drug interactions (including drug/drug, drug/food, drug/device and drug/alcohol)

When a patient is not exposed to a marketed medicinal product, but the physician/consumer becomes aware of the potential for a medication error, or an intercepted medication error, this should also be reported.

11. PUBLICATION OF DATA AND PROTECTION OF TRADE SECRETS

Regardless of the outcome of a study, the marketing authorization holder is dedicated to openly providing information on the study to healthcare professionals and to the public, both at scientific congresses and in peer-reviewed journals. The marketing authorization holder will comply with all requirements for publication of study results.

The results of this study may be published or presented at scientific meetings. If this is foreseen, the physician must agree to submit all manuscripts or abstracts to the marketing authorization holder prior to submission for publication or presentation. This allows the marketing authorization holder to protect proprietary information and to provide comments based on information from other studies that may not yet be available to the physician.

In accordance with standard editorial and ethical practice, the marketing authorization holder will generally support publication of multicenter studies only in their entirety and not as individual center data. In this case, a coordinating physician will be designated by mutual agreement.

Authorship will be determined by mutual agreement and in line with International Committee of Medical Journal Editors' authorship requirements. Any formal publication of the study in which contribution of marketing authorization holder personnel exceeded that of conventional monitoring will be considered as a joint publication by the physician and the appropriate marketing authorization holder personnel.

Any inventions and resulting patents, improvements, and/or know-how originating from the use of data from this study will become and remain the exclusive and unburdened property of the marketing authorization holder, except where agreed otherwise.

[REDACTED]

[REDACTED]

[REDACTED]

[REDACTED]

Appendix 2 Data Collection Overview (as per Standard of Care)

Data Collection (available data will be collected; no additional diagnostic or monitoring procedures shall be applied to the patients outside of routine clinical practice)	Baseline	Data Collected during Observational Period	End of Treatment	Data Collected during Follow-Up
Inclusion/exclusion criteria ^a	x			
Demographic data ^b	x			
ECOG PS	x	x	x	x
Elevated LDH level within 1 month before cobimetinib / vemurafenib initiation	x			
Quality of Life (EORTC QLQ C30)	x	x	x	
Medical history ^c	x			
Melanoma history ^d	x			
Concomitant medication	x	x	x	
Start date of therapy with cobimetinib / vemurafenib	x			
Start and end date of treatment interruption (if appl.)		x	x	
Start and end date of dose modification (if appl.)		x	x	
Information on dose modification ^e (if appl.)		x	x	
Reason for dose modification / treatment interruption (if appl.)		x	x	
Concomitant local treatment for brain metastasis ^f (if appl.)		x	x	
Tumor Response (CR, PR, SD, PD) ^g		x	x	
Elevated LDH level during therapy / follow up		x	x	x
Date of disease progression		x	x	
Stop date of therapy with cobimetinib / vemurafenib		x	x	
Reason for Discontinuation ^h		x	x	
AEs, SAE, AEs of interest, Pregnancies		x	x	x
Therapy following cobimetinib / vemurafenib (if appl.)				x
Tumor Response to following therapy (CR, PR, SD, PD) ^g				x
Date of death		x	x	x
Reason for death ⁱ		x	x	x

- ^a Inclusion criteria: Date of informed consent, age \geq 18 years, date of histologically confirmed malignant melanoma, AJCC stage IIIC unresectable or IV, date of positive BRAF V600 mutation analysis; exclusion criteria: no previous with BRAF- and/or MEK inhibitors prior to study entry, no Hypersensitivity to the active substances or to any of the excipients listed in appendix 4
- ^b Demographic data include age, sex, and self-reported race/ethnicity.
- ^c Medical history including significant diseases within the previous 3 years, major surgeries.
- ^d Melanoma history (including information on primary melanoma [date of diagnosis, histologic type, site, Breslow's thickness], BRAF mutation status, date of first diagnosis AJCC stage IIIC unresectable or stage IV, current AJCC stage; prior adjuvant and palliative therapies for melanoma, number of extracranial metastatic sites at baseline; in case of brain metastasis: date of first diagnosis of brain metastasis, prior local treatment for brain metastasis, number of brain metastases, largest diameter, symptomatic/asymptomatic brain metastasis, leptomeningeal disease, concomitant medication for brain metastases [i.e. steroids, anticonvulsants])
- ^e dosage and dosing schedule of cobimetinib / vemurafenib
- ^f Concomitant local treatment for brain metastasis (including type of treatment [i.e. surgery, radiotherapy], type of radiotherapy [i.e. whole brain radiotherapy, whole brain radiotherapy with boost, stereotactic radiotherapy], total dose and fraction of radiotherapy, number of metastases treated, steroid use prophylactic or therapeutic)
- ^g according to clinical practice
- ^h PD, AE/SAE, patient's wish, response, physician's decision
- ⁱ Due to melanoma (yes/no/unknown)

Appendix 3 Methods for Assessing and Recording Adverse Events

3.1 Assessment of Severity of Adverse Events

3.2 Assessment of Causality of Adverse Events

3.3 Procedures for recording Adverse Events

Appendix 3.1 Assessment of Severity of Adverse Events

The AE severity grading scale for the NCI CTCAE (v4.0) will be used for assessing AE severity. The table below will be used for assessing severity for AEs that are not specifically listed in the NCI CTCAE.

Adverse Event Severity Grading Scale

Grade	Severity
1	Mild; asymptomatic or mild symptoms; clinical or diagnostic observations only; or intervention not indicated
2	Moderate; minimal, local, or non-invasive intervention indicated; or limiting age-appropriate instrumental activities of daily living ^a
3	Severe or medically significant, but not immediately life-threatening; hospitalization or prolongation of hospitalization indicated; disabling; or limiting self-care activities of daily living ^{b, c}
4	Life-threatening consequences or urgent intervention indicated ^d
5	Death related to AE ^d

Note: Based on the NCI CTCAE (v4.0), which can be found at:

http://ctep.cancer.gov/protocolDevelopment/electronic_applications/ctc.htm

^a Instrumental activities of daily living refer to preparing meals, shopping for groceries or clothes, using the telephone, managing money, etc.

^b Examples of self-care activities of daily living include bathing, dressing and undressing, feeding oneself, using the toilet, and taking medications, as performed by patients who are not bedridden.

^c If an event is assessed as a “significant medical event,” it must be reported as an SAE (see Section 10.1.3.1 for reporting instructions), per the definition of SAE in Section 10.1.1.2.1.

^d Grade 4 and 5 events must be reported as SAEs (see Section 10.1.3.1 for reporting instructions), per the definition of SAE in Section 10.1.1.2.1.

Appendix 3.2 Assessment of Causality of Adverse Events

Physicians should use their knowledge of the patient, the circumstances surrounding the event, and an evaluation of any potential alternative causes to determine whether or not an AE is considered to be related to the study medicine, indicating “yes” or “no” accordingly. The following guidance should be taken into consideration:

- Temporal relationship of event onset to the initiation of study medicine
- Course of the event, considering especially the effects of dose reduction, discontinuation of study medicine, or reintroduction of study medicine (when applicable)
- Known association of the event with the study medicine or with similar treatments
- Known association of the event with the disease under study
- Presence of risk factors in the patient or use of concomitant medications known to increase the occurrence of the event
- Presence of non-treatment-related factors that are known to be associated with the occurrence of the event

For patients receiving combination therapy, causality will be assessed individually for each of the medicinal product.

Appendix 3.3 Procedures for recording Adverse Events

Appendix 3.3.2 Diagnosis versus Signs and Symptoms

For AEs, a diagnosis (if known) should be recorded in the AE section of the CRF rather than individual signs and symptoms (e.g., record only liver failure or hepatitis rather than jaundice, asterixis, and elevated transaminases). However, if a constellation of signs and/or symptoms cannot be medically characterized as a single diagnosis or syndrome at the time of reporting, each individual event should be recorded in the AE section of the CRF. If a diagnosis is subsequently established, all previously reported AEs based on signs and symptoms should be nullified and replaced by one AE report based on the single diagnosis, with a starting date that corresponds to the starting date of the first symptom of the eventual diagnosis.

Appendix 3.3.3 Adverse Events Occurring Secondary to Other Events

In general, AEs that are secondary to other events (e.g., cascade events or clinical sequelae) should be identified by their primary cause, with the exception of severe or serious secondary events. A medically significant secondary AE that is separated in time from the initiating event should be recorded as an independent event in the AE section of the CRF. For example:

- If vomiting results in mild dehydration with no additional treatment in a healthy adult, only vomiting should be reported on the CRF.
- If vomiting results in severe dehydration, both events should be reported separately on the CRF.
- If a severe gastrointestinal hemorrhage leads to renal failure, both events should be reported separately on the CRF.
- If dizziness leads to a fall and subsequent fracture, all three events should be reported separately on the CRF.
- If neutropenia is accompanied by an infection, both events should be reported separately on the CRF.

All AEs should be recorded separately in the AE section of the CRF if it is unclear as to whether the events are associated.

Appendix 3.3.4 Persistent or Recurrent Adverse Events

A persistent AE is one that extends continuously, without resolution, between patient evaluation timepoints. Such events should only be recorded once in the AE section of

the CRF. The initial severity (intensity or grade) of the event will be recorded at the time the event is first reported. If a persistent AE becomes more severe, the most extreme severity should also be recorded in the AE section of the CRF. If the event becomes serious, it should be reported to the marketing authorization holder immediately (i.e., no more than 24 hours after learning that the event became serious; see Section 10.1.3.1 for reporting instructions). The AE section of the CRF should be updated by changing the event from "non-serious" to "serious," providing the date that the event became serious, and completing all data fields related to SAEs.

A recurrent AE is one that resolves between patient evaluation timepoints and subsequently recurs. Each recurrence of an AE should be recorded separately in the AE section of the CRF.

Appendix 3.3.5 Abnormal Laboratory Values

Not every laboratory abnormality qualifies as an AE. A laboratory test result must be reported as an AE if it meets any of the following criteria:

- Is accompanied by clinical symptoms
- Results in a change in study treatment (e.g., dosage modification, treatment interruption, or treatment discontinuation)
- Results in a medical intervention (e.g., potassium supplementation for hypokalemia) or a change in concomitant therapy
- Is clinically significant in the physician's judgment

Note: For oncology studies, certain abnormal values may not qualify as AEs.

It is the physician's responsibility to review all laboratory findings. Medical and scientific judgment should be exercised in deciding whether an isolated laboratory abnormality should be classified as an AE.

If a clinically significant laboratory abnormality is a sign of a disease or syndrome (e.g., alkaline phosphatase and bilirubin 5 ´ the upper limit of normal [ULN] associated with cholestasis), only the diagnosis (i.e., cholestasis) should be recorded in the AE section of the eCRF.

If a clinically significant laboratory abnormality is not a sign of a disease or syndrome, the abnormality itself should be recorded in the AE section of the CRF, along with a descriptor indicating if the test result is above or below the normal range (e.g., "elevated potassium," as opposed to "abnormal potassium"). If the laboratory abnormality can be characterized by a precise clinical term per standard definitions, the clinical term should be recorded as the AE. For example, an elevated serum potassium level of 7.0 mEq/L should be recorded as "hyperkalemia."

Observations of the same clinically significant laboratory abnormality from visit to visit should only be recorded once in the AE section of the eCRF (see Appendix 3.3.4 for details on recording persistent AEs).

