7.2 OBJECTIVES

The primary objective for this study is as follows:

- to estimate OS according to cohorts with cerebral and without cerebral metastases (investigator assessed)

The secondary objectives for this study are as follows:

- to estimate intermediate endpoints, including:
 - PFS (investigator assessed)
 - ORR (CR + PR) (investigator assessed)
 - Intracranial ORR (iORR)
 - Extracranial ORR (eORR)
 - Time to CNS relapse in cohort with cerebral metastases / development of cerebral metastases in cohort with solely extracerebral metastases (investigator

assessed)

- to describe clinical characteristics of patients overall, and according to both cohorts (i.e. demographic data, medical history, information on primary mM, ECOG performance status, serum LDH at baseline, number of extracranial metastatic sites at baseline; in case of brain metastasis: number of brain metastases, largest diameter, symptomatic/asymptomatic brain metastasis, leptomeningeal disease, concomitant therapy for brain metastasis)
- to describe utilization of cobimetinib / vemurafenib (type and number of previous adjuvant and palliative treatments, dosing schedules, treatment beyond progression, reason for discontinuation, subsequent therapies and concomitant medication)
- to describe utilization of cobimetinib / vemurafenib and treatment for brain metastasis (prior local treatment for brain metastases, concomitant radiotherapy or surgery, type of radiotherapy, steroid use prophylactic or therapeutic, use of anticonvulsiva)
- to describe patient reported outcome using the EORTC QLQ-C30 questionnaire

Safety Objectives

The safety objectives for this study are as follows:

The incidence of all adverse events (AEs) and serious adverse events (SAEs) in cobimetinib / vemurafenib treated patients.

- All protocol-specified adverse events (AEs) described in this section will be reported and graded according to the National Cancer Institute Common Terminology Criteria for Adverse Events version 4 (CTCAE v4.03).
- Incidence and outcomes of serious and non-serious AEs of interest (i.e., those AEs identified by Genentech/Roche as potential or known risks of cobimetinib and/or vemurafenib use)
- These AEs of interest for the combination of vemurafenib and cobimetinib include the following:
 - Any grade serous retinopathy
 - Any grade retinal vein occlusion
 - Grade \geq 2 left ventricular dysfunction

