- Rhabdomyolysis grade ≥ 3 CPK elevation (including elevations of CPK-MM in conjunction with other laboratory evidence (aldolase and urine myoglobin), clinical features consistent with rhabdomyolysis such as muscle pain, sings or renal failure, or dark red or brown urine)
- Grade ≥ 3 hemorrhage event or any grade cerebral hemorrhage
- Grade ≥ 3 rash
- Grade ≥ 3 photosensitivity
- Events suggestive of drug induced liver injury or other Grade ≥ 3 hepatotoxicity as defined by:
 - o Grade ≥ 3 elevations of aspartate aminotransferase (AST), alanine aminotransferase (ALT), serum bilirubin, gamma-glutamyl transpeptidase/transferase (GGT), OR cases of elevated ALT or AST in combination with either an elevated bilirubin or clinical jaundice
- AE potentially associated with prolongation of cardiac repolarization
- New or progression of RAS mutant malignancy, cutaneous squamous cell carcinoma, new primary melanoma, or basal cell carcinoma, or other new malignancies.

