10.1.1.1 Adverse Events

According to the International Conference of Harmonisation (ICH), an AE is any untoward medical occurrence in a patient or clinical investigation subject administered a pharmaceutical product, regardless of causal attribution. An AE can therefore be any of the following:

- Any unfavorable and unintended sign (including an abnormal laboratory finding), symptom, or disease temporally associated with the use of a medicinal product, whether or not considered related to the medicinal product
- Any new disease or exacerbation of an existing disease (a worsening in the character, frequency, or severity of a known condition), except as described in Appendix 3
- Recurrence of an intermittent medical condition (e.g., headache) not present at baseline
- Any deterioration in a laboratory value or other clinical test (e.g., electrocardiogram [ECG], X-ray) that is associated with symptoms or leads to a change in study treatment or concomitant treatment or discontinuation from study medicine.

10.1.1.2 Assessment of Serious Adverse Events (Immediately Reportable to the Marketing Authorization Holder), Non-serious Adverse Events of Special Interest (AESI) and Other Non-serious Adverse Events

Serious Adverse Events

An SAE is any AE that meets any of the following criteria:

- Is fatal (i.e., the AE actually causes or leads to death)
- Is life-threatening (NOTE: The term “life-threatening” refers to an event in which the patient was at immediate risk of death at the time of the event; it does not refer to an event that hypothetically might have caused death if it were more severe.)
- Requires or prolongs inpatient hospitalization (see A)
- Results in persistent or significant disability/incapacity (i.e., the AE results in substantial disruption of the patient’s ability to conduct normal life functions)
- Is a congenital anomaly/birth defect in a neonate/infant born to a mother exposed to study medicine
- Is a significant medical event in the physician’s judgment (e.g., may jeopardize the patient or may require medical/surgical intervention to prevent one of the outcomes listed above)

The terms “severe” and “serious” are not synonymous. Severity refers to the intensity of an AE (e.g., rated as mild, moderate, or severe, or according to NCI CTCAE criteria; see Appendix 3); the event itself may be of relatively minor medical significance (such as severe headache without any further findings).

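### The recording rule for laboratory values has no grade trigger, so isolated Grade 3 liver values that Section 7.2 counts as AEs of interest can go unrecorded and cannot be recovered later

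*Protocol*

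**What the plan says.** **The objective and the event definitions.** Protocol Section 7.2 lists as a safety objective "Incidence and outcomes of serious and non-serious AEs of interest". It also states: "All protocol-specified adverse events (AEs) described in this section will be reported and graded according to the National Cancer Institute Common Terminology Criteria". Among the events it then names are "Grade ≥ 3 elevations of aspartate aminotransferase (AST), alanine aminotransferase (ALT), serum bilirubin" or GGT, with no condition on symptoms, action or judgement. Combined elevations of a transaminase with bilirubin or jaundice are a separate alternative. The muscle item begins "Rhabdomyolysis grade ≥ 3 CPK elevation" and runs on into a bracket that mixes laboratory evidence with clinical features. The synopsis repeats the list.

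**The recording rule.** Section 10.1.2 ties recording to the AE definition in Section 10.1.1.1, and Section 10.1.2.2 sends sites to Appendix 3 for abnormal laboratory values. Appendix 3.3.5 says: "A laboratory test result must be reported as an AE if it meets any of the following criteria". The four criteria are accompanying symptoms, a change in study treatment, a medical intervention or change in concomitant therapy, and clinical significance as the physician sees it. It adds "Note: For oncology studies, certain abnormal values may not qualify as AEs" and leaves isolated abnormalities to medical and scientific judgement. The laboratory item of Section 10.1.1.1 is conditional in a similar way: "Any deterioration in a laboratory value or other clinical test (e.g., electrocardiogram [ECG], X-ray) that is associated with symptoms or leads to a change". The change may concern study or concomitant treatment, or be a stop of study medicine.

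**The data collected.** Section 8.4.2 limits documented results to the assessments it goes on to list. In that list and in Appendix 2 the only laboratory value is LDH, for example "Elevated LDH level during therapy / follow up". AEs of interest appear as a data item of their own.

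**The concern.** The objective counts events by laboratory grade, while the rule that decides what enters the database does not look at grade. A patient with an isolated Grade 3 ALT, no symptoms, unchanged treatment and a physician who thinks it unimportant meets the Section 7.2 definition, yet none of the Appendix 3.3.5 criteria is met.

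Two things are at stake. First, the reported incidence of these events may reflect local habits of judgement at about 40 centers rather than the grade that defines the event. Section 8.9 says data will be collected consistently so as to avoid bias, and this rule works against that. Second, because the underlying values are not collected, no analysis plan could rebuild the events afterwards.

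**Working it through.** The protocol gives no expected incidence, precision or sample size for these events, so there is no figure of its own to reproduce. The check is mainly a comparison of passages.

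**1. Which Grade ≥ 3 values must be recorded in any case?**
- Values with symptoms, a treatment change, an intervention, a concomitant-therapy change or judged clinical significance: yes (Appendix 3.3.5).
- ALT or AST above 3 × ULN together with bilirubin above 2 × ULN or jaundice: yes (Appendix 3.3.7; also an AESI in Section 10.1.1.2).
- Grade 4 liver tests: yes (AESI list, Section 10.1.1.2).
- Other Grade 4 values such as CPK: a footnote in Appendix 3.1 makes Grade 4 events SAEs, but it belongs to the AE severity scale and so presupposes that the value already counts as an AE.
- Isolated Grade 3 AST, ALT, bilirubin or GGT meeting none of the four criteria: no passage of the recording rules requires entry. The AESI list does not name them, and it has no CPK entry at all.

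**2. Can a missed value be recovered?** No. LDH is the only laboratory value in Section 8.4.2 and Appendix 2. Section 8.4.5 and Appendix 3.3.15 mention safety data other than AEs but refer to Section 8.3, where the safety variables are all adverse events.

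**3. Is CPK in the same position?** Only on one reading. The item can mean rhabdomyolysis or any Grade ≥ 3 CPK rise, or only rhabdomyolysis with such a rise. The liver tests carry the point without it.

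**4. Direction and possible size.** Let p be the true incidence, s the share of events that are isolated Grade 3 values meeting none of the three objective criteria, and c the share of those that physicians still record. Then

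recorded incidence = p × [1 − s × (1 − c)].

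The planned enrolment of 225 comes from Section 8.5. The values of p, s and c are assumptions for illustration; the protocol gives none of them. Example: 0.10 × [1 − 0.5 × (1 − 0.5)] = 0.075, and 225 × 0.075 = 16.9 patients, against 225 × 0.10 = 22.5.

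| Assumed p | c = 1, any s | s = 0.5, c = 0.5 | s = 0.5, c = 0 | s = 0.75, c = 0 |
|---|---|---|---|---|
| 5% | 5.0% | 3.75% | 2.5% | 1.25% |
| 10% | 10.0% | 7.5% | 5.0% | 2.5% |
| 15% | 15.0% | 11.25% | 7.5% | 3.75% |

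The bracket never exceeds 1, so this mechanism can only lower the count. At c = 1 the loss is zero.

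**The case against.** The strongest reply is that the protocol already imposes the duty. Section 7.2 says the events it describes will be reported and graded, and AEs of interest are a separate item in Section 8.4.2 and Appendix 2. Appendix 3.3.5 says when a result must be reported; it does not forbid reporting others. The first item of the AE definition in Section 10.1.1.1 admits an abnormal laboratory finding without further condition. On this view a site that enters nothing has complied with the appendix but not with Section 7.2.

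That stands in part. A reader might infer that sites are under no duty to record these values, and the documents do not support so much. What they show is a conflict: one section says the events will be reported, while the specific instruction on laboratory values, to which sites are directed, leaves isolated values to judgement.

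It can also be argued that a value below the AE threshold is not a missed AE. This weakens any claim about the overall rate of Grade ≥ 3 AEs in Section 8.3.3, since that variable counts only what qualifies as an AE. It is less convincing for the liver events, which Section 7.2 defines by grade without a further condition.

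Finally, judgement-based reporting of laboratory AEs is a usable convention in a study that documents routine care, and Section 8.9 lists information bias and missing data as limitations. But a general limitation does not tell a site which of two instructions to follow.

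**Conclusion.** The point holds as a conflict between the event definition and the recording rule, confined to isolated Grade 3 AST, ALT, bilirubin and GGT values that cause no symptoms, prompt no action and are judged not clinically significant. CPK joins them if its item means any Grade ≥ 3 rise.

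Two stronger readings are tempting. One is that all Grade ≥ 3 laboratory events escape recording; the AESI list and Appendix 3.3.7 rule that out. The other is that incidence is undercounted by some stated amount. The protocol permits undercounting that varies by site, but it neither shows that it occurs nor allows it to be sized: the percentages above rest wholly on assumed inputs, and the loss may be nil.

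It is still worth correcting, because a stated safety objective depends on it and a value not entered during data collection cannot be derived afterwards.

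**What to change.** Add a criterion to Appendix 3.3.5 and mirror it in Section 10.1.1.1: *any laboratory value measured in routine care that meets the definition of an AE of interest in Section 7.2 or of an AESI in Section 10.1.1.2 is recorded as such, whether or not another criterion applies.* The oncology note can remain if it is made subject to this criterion. State whether the CPK item means an isolated Grade ≥ 3 rise or only rhabdomyolysis.

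An alternative is to add available CPK, AST, ALT, bilirubin and GGT results to Section 8.4.2 and Appendix 2, so that incidence can be derived from the values.

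The first route costs one sentence in two places and site training; the second costs more data entry. Neither adds tests, so the non-interventional design is untouched. The downside of the first is more AE entries for asymptomatic values and somewhat higher reported rates. Patients not tested in routine care remain unobserved under either route, which should be stated as a limitation.
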